# Work Package 2:

*Objective 3:* To develop a sexual risk assessment/triage tool to identify service users' level of sexual risk and thus individualise packages of behavioural interventions to users' need.

**Study design:** Sexual risk assessment/triage tools will be developed to identify individuals at increased risk of STIs and HIV, through the analysis of routinely collected demographic, clinical and behavioural data that is entered into electronic patient records (EPR) as part of routine care in SH services and captured in the Genitourinary Medicine Clinic Activity Dataset (GUMCAD).

Statistical analysis of GUMCAD the latest version of which (GUMCADv3) will link individuals' sociodemographic, geographical, clinical and behavioural data with their incident or prevalent STIs (including HIV) will be undertaken to determine which factors best predict subsequent STI acquisition. GUMCAD is a pseudoanonymised patient-level electronic dataset which collects information on diagnosis made and other commissioned services provided by genitourinary medicine (GUM) clinics (level 3 services). The extension of GUMCAD to include information from other commissioned non-GUM sexual health services (level 2 services such as enhanced GPs, integrated contraception and sexual health services, young people's services e.g. Brook clinics, and other third sector or volunteer sectors services) is being rolled out (GUMCADv2). Collection and reporting of GUMCADv2 (n=570) from all level 2 and 3 services to PHE is mandatory; this therefore will be the **study population and setting** for this component of the analysis.

The **data collected** in GUMCADv2 includes basic demographic information (age, gender, self-defined ethnicity, country of birth, and sexual orientation) and residence (lower-level super output area of residence [LSOA] based on postcode), clinic information (which clinic and type of appointment), clinical information including all tests, vaccinations and diagnoses made for all patients seen. The STI diagnoses recorded include gonorrhoea or chlamydia including complicated and uncomplicated by site of infection), trichomonas, syphilis (including stage), genital herpes (primary or recurrent), genital warts (primary or recurrent), HIV and other blood borne viruses, and whether or not the patient was a contact of partner with an STI.

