**Data analysis:** Ordinal regression models to identify a parsimonious model of the key predictors of sexual risk according to the hierarchy above and thus the variables that an algorithm should take into account. These models will be informed by a social determinants framework (Monteiro et al 2005, Stenger et al 2013), which acknowledges the role of contextual factors, socio-demographic and geo-spatial (residence as well as clinic attended), in addition to self-reported sexual behaviour and drug and alcohol use to identify people at risk. The analysis (and thus the resulting models) will be disaggregated by gender, ethnicity and sexuality. The algorithm will be developed on a random sample of half the GUMCADv3 pilot dataset and then validated for performance on the remaining half.

**Sample size:** GUMCADv3 pilot data is being collected from 10 clinics, a mixture of types across England, from August 2013. The total number of patients seen annually in these clinics is approximately 140,000 with approximately 35,000 new STIs diagnosed. The large dataset will provide high power to detect associations and validate potential algorithms.

*Outputs:* the outputs of WP2 will include: A risk assessment tool which can be delivered via EPR. The acceptability and feasibility of the tool to identify individuals at three levels of risk in clinical settings will be piloted during WP5.

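### The triage algorithm is validated only on a random half of the same 10 clinics, so its performance in other sexual health clinics is left untested

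*Protocol*

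**What the plan says.** All references are to the Protocol.

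- **Work Package 2, Data analysis (validation).** "The algorithm will be developed on a random sample of half the GUMCADv3 pilot dataset and then validated for performance on the remaining half".
- **Work Package 2, Data analysis (predictors).** The ordinal models are informed by a framework that recognises "contextual factors, socio-demographic and geo-spatial (residence as well as clinic attended"), alongside self-reported sexual behaviour and drug and alcohol use.
- **Work Package 2, Sample size.** "GUMCADv3 pilot data is being collected from 10 clinics, a mixture of types across England, from August 2013". The yearly volume at these sites is put at about 140,000 attenders and 35,000 new infections. The adequacy of the validation is argued from patient numbers alone: "The large dataset will provide high power to detect associations and validate potential algorithms".
- **Work Package 2, Study design.** "Collection and reporting of GUMCADv2 (n=570) from all level 2 and 3 services to PHE is mandatory", and these services are named as the study population and setting.
- **Project outputs, item 2.** The deliverable is a risk algorithm adapted to sexual health clinics. It takes account of the patient's risk profile and of the service attended.
- **Work Package 5.** The tool goes into the electronic records of the participating clinics. Nine pilot clinics are planned, six intervention and three control. Whether any of them belong to the 10 GUMCADv3 clinics is not stated.

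**The concern.** A random half of one dataset contains the same clinics as the other half. Whatever is particular to those 10 clinics is learned in development and met again in validation. This can include local prevalence, case mix, testing habits and how behaviour is recorded. The exercise answers whether the model overfits within these clinics. It does not answer whether the model works in a clinic it has not seen, which is what a tool meant for services nationally needs to show.

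The problem is sharper if clinic identity becomes a model term. Such a term has no estimated value for a clinic outside the 10, yet it improves the apparent fit in the validation half.

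Nothing later closes the gap. The Work Package 5 outcomes count patients triaged, offered, accepting and completing the intervention, and none compares the risk category with a later STI diagnosis. Work Package 6 refines the tool without a planned check of predictive performance. The internal figure would therefore be the only evidence on performance carried towards a full trial.

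**Working it through.** The plan states no performance target or validation sample size, so there is no figure of its own to reproduce. The check uses the stated counts, and then a simulation whose inputs are assumptions.

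**1. Precision within the 10 clinics is not the issue.**
- New STIs per patient seen: 35,000 / 140,000 = 0.25. This is used as a rough prevalence; it is a ratio of diagnoses to patients.
- Each half, per year of data: 140,000 / 2 = 70,000 patients and 35,000 / 2 = 17,500 STIs.
- Standard error of a 25% prevalence in the validation half: √(0.25 × 0.75 / 70,000) = 0.0016, or 0.16 percentage points.
- Clinics in the validation half that were not used in development: in practice 0 of 10.

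**2. What a same-clinic split cannot reveal.** Let clinics vary around logit(0.25) = ln(1/3) with between-clinic SD s. The 95% range of prevalence for a new clinic is expit(ln(1/3) ± 1.96 s). The value of s is assumed.

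| s | 95% range, new clinic |
|---|---|
| 0.2 | 18% to 33% |
| 0.5 | 11% to 47% |
| 0.8 | 7% to 62% |

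This is the spread before patient-level predictors explain any of it.

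**3. Illustrative simulation.** Ten clinics of 14,000 patients; logit = −1.25 + 0.75x + u, with one patient predictor x and clinic effect u with SD s. Calibration error is the absolute difference between observed and mean predicted prevalence in a clinic, averaged over clinics. Three analyses are compared: a random half with clinic terms, a random half without them but tabulated by clinic, and leave-one-clinic-out.

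| s | Random half, clinic terms | Random half, no clinic terms, by clinic | Leave-one-clinic-out |
|---|---|---|---|
| 0.3 | about 0.6 points | 3.9 points | 4.4 points |
| 0.5 | about 0.6 points | 6.4 points | 7.1 points |

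Repeated runs moved the last two columns a little. Over both values of s, the random half without clinic terms gave 3.7 to 7.1 points, and leave-one-clinic-out gave 4.1 to 7.8.

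Discrimination changes less. With clinic terms the random-half AUC is 0.71 to 0.72, against about 0.68 to 0.69 for unseen clinics. Without clinic terms the AUC barely differs between the two methods.

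**4. Pooled results and the null case.** A second simulation developed the model with clinic terms in 10 clinics and applied it, with the average clinic effect, to nine new ones. The pooled observed/expected ratio in the random half stayed near 1.00 at every s.

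| s | AUC, random half | AUC, new clinics | Mean lowest and highest observed/expected, nine new clinics |
|---|---|---|---|
| 0 | 0.68 | 0.68 | 0.95 and 1.06 |
| 0.2 | 0.69 | 0.68 | 0.79 and 1.24 |
| 0.5 | 0.71 | 0.68 | 0.57 and 1.61 |

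So a pooled summary can look perfect while single clinics are well off. When clinics do not differ, the two validations agree.

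**The case against.** The strongest reply is that the large contrast depends on a model the protocol does not commit to. The clinic attended is named within a framework that informs the models, not as a fixed term. The same section seeks a parsimonious model, and clinic type would fit the text equally well. Without clinic terms, a random half tabulated by clinic shows nearly the same spread as leave-one-clinic-out (6.4 against 7.1 points at s = 0.5). Tabulating by clinic is the kind of detail an analysis plan may hold. The planned models also have many more predictors than the simulation and are disaggregated by gender, ethnicity and sexuality, so they may absorb much of the between-clinic difference. This stands, and it makes the size conditional. It does not turn a same-clinic split into a test in new clinics.

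A reader might infer more than the documents support:

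- **That the validation says nothing about the clinics that will use the tool.** Overlap between the 10 GUMCADv3 clinics and the nine pilot clinics is not stated. For any shared clinic the split is informative.
- **That the low, medium and high cut-offs would be miscalibrated.** No probability cut-offs are given. The three levels are outcome categories defined by diagnosis.
- **That the result drives the Work Package 5 sample size.** That calculation rests on the proportion completing the intervention. The proportion classified medium or high risk is also measured directly in each of the six implementing centres.
- **That halving the data, or having the same patient in both halves, does material harm.** About 70,000 patients per half is ample overall, and the dataset is described as patient-level.

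Finally, this is development work ahead of a feasibility study, and the protocol does not claim external validity. That bears on urgency, not on whether the better method should be used.

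**Conclusion.** The concern holds in a limited form. The planned validation is internal only. It leaves untested how the algorithm performs in clinics outside the 10, and no later step supplies that test.

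If clinic identity is a term, the random half will look well calibrated in every clinic: about 0.6 points of error, against about 4 to 8 points for an unseen clinic at an assumed between-clinic SD of 0.3 to 0.5. If it is not a term, the split conceals the between-clinic spread only when performance is pooled. If clinics do not differ, nothing is concealed.

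The change should be made. Confidence is moderate, because the protocol gives neither the between-clinic variation nor the form in which clinic enters the model, and the simulated sizes are illustrations rather than estimates for this dataset.

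**What to change.** Replace the random-half split by internal-external cross-validation over the 10 clinics: leave out each clinic in turn, develop the model on the other nine, and assess it in the one left out. Report discrimination and calibration for each held-out clinic, with their spread, and not only a pooled figure. Use clinic features that carry over to a new site, such as type and region, in place of clinic identity. Refit the final model on all the data. It would also help to state which of the Work Package 5 clinics, if any, are among the 10.

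The cost is a change of analysis wording and a little computing on the same dataset, with no new data. There are two drawbacks. Reported performance may look less favourable. Some strata of gender, ethnicity and sexuality within a single held-out clinic will be sparse, so results for those strata may have to be combined across clinics.

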# Work Package 3:

*Objectives 4*: To describe current practice and preferences in UK sexual health (SH) clinics with respect to delivery of sexual risk reduction interventions and identify best practice.

*Objective 5:* To explore opportunities and challenges to delivery of candidate risk reduction interventions in SH clinics

*Study design:* A series of linked studies using mixed methods: key informant interviews, semi-structured interviews with service users, a national internet-based survey of service leads, and a discrete choice experiment among service users, as follows:

*i. Key informant interviews:* to be conducted by telephone. The **target population** from whom a purposive sample will be taken comprises HCP, including service leads, health advisors, and clinicians (doctors and nurses). The **settings** will include 15 clinics purposively selected to include a range of type, size, location, and client mix. A **sample** of n=30 will be recruited to complete semi-structured interviews exploring the following themes (to be informed by WP1 and 2):

- the types and extent of triage methods in use and who does it.
- the behavioural interventions delivered and who delivers it (including 1:1 structured discussion to address risk taking as per NICE guidelines).
- the organisation of staff, time and resources spent on risk reduction interventions.
- the acceptability and feasibility of introducing a triage tool and the candidate interventions.

*ii. Semi-structured interviews with patients:* to be conducted as face-to-face interviews with a purposive sample of a **target population** of young men and women, and MSM, recruited at different points in the clinic pathway, with and without a diagnosed STI, and from **settings** comprising a range of clinic types and locations, from a range of ages and ethnicities. A **sample** of n=30 will be recruited to explore the following themes

- experience of the clinical service on the day- including the pathways of care
- attitude towards risk assessment
- own perception of their sexual risk
- experience of behavioural interventions in the past
- preference for behavioural interventions, if any

*iii. Internet survey:* a brief (10 minute) web-based survey. The **target population** will be SH clinic service leads who report to GUMCADv2 (n=570). It will be informed by the data emerging from the qualitative study with clinic staff in order to provide an overview of clinic practice in the UK. In order to maximise the response rate there will be liaison with the British Association of Sexual Health and HIV (BASHH), as the survey data will provide an opportunity to audit risk reduction strategies in sexual health settings, as per NICE guidelines. **Data collected** will include:

- clinic staff size and distribution
- distribution of clinical tasks amongst staff groups
- the proportion of clinics that conduct a risk assessment on patients
- the staff groups that are involved in the risk assessment.
- the proportion of clinics which deliver 1:1 structured discussion to address risk, as per NICE guidelines
- the staff groups that deliver the intervention and the training that they have
- types of interventions used, behaviour change techniques used and delivery modes
- the proportion of patients who receive this intervention
- the resource allocated to these interventions

For the purpose of **data analysis**, all interviews will be recorded and transcribed; content analysis will be conducted independently by a minimum of two researchers and discrepancies in coding will be resolved through discussion until a consensus is reached. Analysis will be conducted using the framework approach. This deductive approach to qualitative analysis allows for a more structured approach to data collection based on predetermined aims and objectives. Software (NVivo version 10) will be used to synthesise and code the data within a thematic matrix to enable elucidation of conceptual associations. Both pre-determined concepts used for developing the topic guides as well as emergent themes arising from the data will inform the process of identifying the key thematic categories to be used in data coding, which will then be used to index and chart findings. The internet survey will be analysed using simple descriptive statistics, adjusted for clinic type, and location.

- 3. Gain ethical approval and administer the DCE instrument
- 4. Analyse the data using appropriate regression techniques given the precise DCE design, and determining the relative importance of the different intervention characteristics.

**Data collected:** The attributes covered by the questionnaire will be informed by the literature review. Attributes and levels will be combined in choice scenarios which the respondents will be asked to choose from. A fractional factorial design (FFD) will be used to create a questionnaire of manageable size while remaining optimal from a statistical perspective (Ryan et al, 2008).

**Target population and setting:** DCEs are not amenable to conventional power calculations, in part because designing the questionnaire (a prerequisite for determining power) is an integral part of the research process. However, other studies using DCE to assess patient preferences for healthcare have typically included 200 participants (Ngene, 2012). Based on previous questionnaire return rates from similar research at sexual health clinics at least 250 participants will be recruited from 6 clinics. Subject to ethical approval, individuals will be recruited from both GUM and CASH clinics. Individuals will be eligible if they are between 16-25 years of age or MSM as they represent the 'high risk' groups of primary interest. No other inclusion or exclusion criteria will be applied but individuals will be asked to provide information regarding variables such as age and other risk factors, at the time of completing the DCE questionnaire. Individuals will be asked to participate in the study by research nurses at the clinics, and to complete a paper based version of the instrument there and then. If individuals do not want to complete the questionnaire at the time, they will be offered the opportunity to complete it online. All data will be collected anonymously.

**Analysis** of the DCE will depend on the exact design, but it is likely to be by random effects logistic regression. Odds ratios and 95% Confidence Intervals (CI) will be used to estimate the relative importance of each attributes level. Preferences for different intervention designs (i.e. combinations of the different attributes) can and will also be presented by presenting the probability individuals would choose one intervention design over another. In order to determine whether preferences differ by respondent characteristics, a second regression model will include interactions between DCE attributes and respondent characteristics (e.g. age, gender, ethnicity and sexual orientation).

*Outputs:* the outputs of WP3 will include: (i) a report describing current practice for risk assessment and intervention in UK sexual health settings; (ii) a list of the candidate interventions and their design that appear popular and deliverable in sexual health settings for further evaluation in WP4 and 5.

# Work Package 4:

*Objective 6:* Using stake holders input, to select, adapt and manualise an evidence-based suite of interventions that can be combined and delivered as intervention packages to meet individuals' needs.

**Study design:** The systematic review from WP1 and the clinical opportunities and user preferences identified in WP3 will be used through a process of Intervention Mapping to select and guide adaptation of a suite of interventions.

A suite of deliverable interventions will be identified and categorised in terms of the particular behaviour change outcomes and self-regulatory skills that they have been found to change effectively. These can then be matched to deficits and behaviour change needs in service users. Candidate interventions will be analysed into their component parts drawing on IM design methods and assessed – and where necessary adapted – for use in UK clinics using a variety of delivery modes including, for example, sexual health clinic waiting rooms (e.g.,

informational videos), one-to-one clinic appointments (e.g., motivational interviewing and skills training), group-based interventions and self-delivered interventions (including interactive digital interventions). For those categorised by the triage tool as at highest risk, one-to-one interventions (e.g. motivational interviewing) are likely to be offered as recommended by NICE (NICE, 2007a). Intervention components are likely to consist of: techniques to provide persuasive information about health consequences, consolidate self-protective values, norms and motivation, set personal goals, promote in-context self-regulation (including if-then planning), undertake self-monitoring and self-assessment, teach persuasive negotiation skills, as well as development of condom-related behavioural skills including accessing, carrying, and using condoms and lubricant, and making condoms more sexually exciting. In addition, where not currently specified by existing interventions, components can be added that enhance motivation to change and other techniques recommended by NICE to be effective at eliciting behaviour change (e.g. intervention components that increase self-efficacy and norms, including peer practices and approval) (NICE behavioural interventions NICE, 2007b). It is envisaged that 'best bet' interventions will be adapted for use with the high risk target groups and amended with PPI and staff input through the use of Focus Groups. For example, existing interventions may be adapted to ensure feasibility of faithful delivery in clinic settings or to optimise maintenance of behaviour change by including the addition of follow up contact where this is supported by evidence provided by WP1, or support partner notification.

Each intervention package will be guided by a manual which will define specific and replicable modes of delivery with underlying behaviour change mechanisms. As there is a need to translate effective behaviour change interventions from research settings to clinical practice, the manual would provide recommendations for the implementation in a clinical context. Finally, constructing guidelines for monitoring the reliability and validity of the interventions will increase the fidelity of the interventions and will be an additional strength of this work.

Intervention Mapping consists of 6 iterative steps: (1) needs assessment, (2) mapping of intervention objectives (i.e., main outcomes) onto psychological, behavioural and environmental determinants or change processes, (3) selecting techniques and strategies to modify the determinants of behaviour based on an understanding of change processes, (4) selection and construction of intervention components and materials, (5) planning for intervention adoption, implementation and sustainability and (6) planning evaluation including process and outcome evaluation methods and instruments. This process will be applied across all work packages. The systematic review (WP1) review will clarify the needs of clinic users and staff in identifying potentially effective interventions and intervention components as well as potential change mechanisms that may be critical to intervention to our main outcomes) in UK clinic settings in order to identify 'best bet' techniques and strategies. This work will help inform the analyses of existing risk reduction clinic practices (WP3). Outputs from WP1, 2 and 3 will provide the evidence base for stage 4 of the IM package that is, selecting and adapting a suite of evidence-based interventions suitable for delivery in UK sexual health clinics (WP4). As this process proceeds, the feasibility study of an RCT (WP5) will be detailed, together with a manual allowing replication of the intervention construction and implementation practices (WP6).

Stage 4 of the intervention mapping process (WP4) will comprise focus groups with current and/or previous service users, a PPI advisory group, sexual health advisors and clinicians. These will be used at the beginning of the IM procedure (months 1-3) to present the front running candidates for inclusion in the intervention suite and to stimulate discussions about: how best to adapt to each group; feasibility of delivery; likely uptake, etc. and thus inform the on-going IM process.

